#### *Inclusion criteria*

Participants are eligible to participate in the study if they fulfill the following inclusion criteria:

- aged 15 or above;  
(**optional:** Each centre has the option to recruit suicide attempters below the age of 15. However, the instruments need to be adopted for the respective age group. Parental consent might be needed for suicide attempters younger than 15 and in some countries younger than 18 to participate in the study).
- attempted suicide who are admitted to the emergency department during the 12-months study period
- proficient in the local language
- consent to participate

#### *Exclusion criteria*

Participants are ineligible to participate for the following criteria:

- clinical condition not allowing for an interview (according to their MDS score)
- leaving against medical advice
- residence in a different catchment area
- inability to communicate in the local language

## BIC Intervention

[figure not shown]
The intervention, including the educational session at discharge and the follow-up procedures, remains unchanged. All participants will receive the BIC intervention in addition to TAU, which is described in the next section. The BIC intervention will include nine follow-ups post discharge (1,2,4, 8, 12 weeks and at 4,6,12 months) with a final 18-months follow-up. Even though, the BIC is a brief one time one-hour motivational awareness increasing interview, there are regular follow-ups of up to 18-months which is a long follow-up.

The BIC intervention will include:

- A. *time of discharge:* an hour individual educational motivational awareness increasing session as close to the time of discharge as possible (the day before or the day of discharge). The information session includes the following:
- ✓ suicidal behavior as a sign of psychological/social distress
  - ✓ risk factors and protective factors
  - ✓ basic epidemiology of suicide and suicide attempt
  - ✓ alternative coping mechanisms instead of destructive behaviours
  - ✓ referrals for treatment or social support

Along with this educational motivational and awareness increasing session, patients will receive two pamphlets highlighting suicide prevention methods and risk factors for suicide (Annex 2- supplied later on).

A. *after discharge*: nine follow-ups via phone calls, physical visits, messaging or using tele-medicine (depending on the site) at:

The follow-ups will be conducted by a volunteer (eg: volunteers from NGOs, individuals working with mental health, community workers, medical students, research assistants), and these volunteers will receive training as well. Follow-ups can be either by phone call, physical visits, tele-medicine or messaging. If a center has the capacity and opportunity to do tele-medicine, tele-medicine should be the preferred follow-up method according to the WHO recommendation. An alternative contact person (eg: a friend or a spouse) who will be knowledgeable about the suicide attempter's outcome and situation will be recorded in case volunteers are unable to reach the patient.

Volunteers will use the follow-up template (Annex 2), also supplied later, that asks the suicide attempter how he/she is doing and if he/she needs any support. If the participant expresses a need for support, he/she will be referred to the appropriate channel. If the suicide attempter doesn't express a need for support, but a risk is noted, referral to an appropriate channel will be suggested.

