**Protocol of BIC study**

This document presents the protocol of Brief Motivational Intervention and Long-term Regular Follow-up Contact Program (BIC), a pre-post study that aims to provide a global treatment action to combat suicide.

The study is based on the WHO protocol of the SUPRE-MISS study, part of the WHO worldwide initiative for prevention of suicidal behaviors (1) and the Veterans Affairs Brief Intervention and Contact Program (VA BIC), a brief educational intervention and regular contacts for patients from a VA mental health unit (2). The current study will use sociodemographic, clinical, and psychosocial questionnaires in suicide attempters presenting at Emergency Departments.

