## II. BIC RCT Study

### Trial design

The study will be a multicenter randomized (1:1) control trial (RCT). Enrolment including eligibility screening and randomization into either the intervention or control group will be conducted according to the WHO randomization methods. Suicide attempters assigned to the COVID-19 BIC group will receive in-person motivational and awareness increasing interview using the COVID-19 BIC method (Annex 1) described separately. These interviews will be conducted by trained health care professionals (eg: a doctor, a nurse, a psychiatrist, a psychologist) one day before or on the day of discharge. The training for the health care professionals will be given on a social media platform where a group training will take place.

Baseline assessments will be conducted after randomization and last follow-up will be 18-month post intervention with intermediate follow-ups by online trained volunteers (eg: volunteers from NGOs, individuals working with mental health, community workers, medical students, research assistants) at the 1, 2, 4, 8, and 12 weeks and then at 4, 6, 12, and 18 months.

A back-up supervisory system will be established to support the health care professionals as well as for the volunteers if they encounter any problems during the interview or during the follow-ups.

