### Primary Outcome

Hypothesis: The BIC will significantly lead to a reduced death by suicide at 18-months follow-up than treatment as usual.

Outcome measure: death from suicide at 18-month follow-up

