There will be follow-up contacts at nine timepoints for those in the intervention group and one follow-up at 18-month for those in the control group. These follow-ups will be conducted using a questionnaire template (Annex 3) and will follow-up if the participant is still live, any consequent suicide attempt, and the well-being of the participant.

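### The protocol describes both a study in which everyone receives BIC and a 1:1 randomised trial against TAU, and does not say which design governs

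*Protocol*

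**What the plan says.** Two places in the protocol point to a single-arm study:

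- The introduction (Protocol of BIC study) calls it "a pre-post study that aims to provide a global treatment action to combat suicide".
- BIC Intervention says "All participants will receive the BIC intervention in addition to TAU". The sentence just before it reads "The intervention, including the educational session at discharge and the follow-up procedures, remains unchanged".

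Five places point to a randomised trial with a TAU-only arm:

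- Trial design specifies a multicentre 1:1 RCT with "randomization into either the intervention or control group", and gives BIC to one of those groups: "Suicide attempters assigned to the COVID-19 BIC group will receive in-person motivational and awareness increasing interview".
- Treatment as Usual treats TAU participants as a group distinct from the intervention group and follows them at 18 months.
- Primary Outcome states the hypothesis: "The BIC will significantly lead to a reduced death by suicide at 18-months follow-up than treatment as usual". The outcome measure is death from suicide at 18 months.
- Evaluation Procedures sets "follow-up contacts at nine timepoints for those in the intervention group and one follow-up at 18-month for those in the control group".
- Sample size asks for at least 1730 participants, 865 per treatment group, assuming 3% suicides on TAU and 1% on BIC, two-sided, with 80% power. The significance level is written as 95%, read here as alpha 0.05.

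No sentence restricts the statement about all participants to one arm, and none says which description takes precedence.

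**The concern.** The two descriptions differ on who receives the intervention and on whether a comparator exists, so they cannot both be carried out. BIC Intervention is also the section that site staff would naturally consult on who gets BIC.

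The primary question is at stake. The hypothesis compares BIC with TAU on suicide death. If everyone receives BIC on top of TAU, no TAU-only participants remain to be compared. A within-person before-after contrast cannot fill the gap, because everyone is alive at enrolment and the outcome has no baseline value. A before-after comparison of cohorts could in principle use suicide death, but the protocol describes no earlier or historical cohort.

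The questionnaire outcomes, such as PHQ-9 and WHO-5, could be analysed as change from baseline. Without a control group, that change would mix any effect of BIC with natural recovery after an attempt and regression to the mean.

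A statistical analysis plan cannot repair this. Who is allocated to what, and whether a control group is enrolled, are settled in the protocol and at the sites.

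**Working it through.** **Inputs** (Sample size section): p1 = 0.03 on TAU, p2 = 0.01 on BIC, alpha 0.05 two-sided, power 80%, allocation 1:1, stated n = 865 per group.

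**Step 1. Which design does the 1730 belong to?** The two-proportion formula with pooled variance under the null, where p = (p1 + p2)/2 = 0.02, is

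n = [1.960 × √(2p(1 − p)) + 0.8416 × √(p1(1 − p1) + p2(1 − p2))]² / (p1 − p2)²

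- First term: 1.960 × √0.0392 = 0.3881
- Second term: 0.8416 × √0.0390 = 0.1662
- n = 0.5543² / 0.0004 = 768.0, or 769 per arm rounded up

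With the continuity correction,

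n' = (n/4) × [1 + √(1 + 4/(n × 0.02))]² = 865.1

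(866 if the rounded-up 769 is carried forward). This reproduces the protocol's 865 per group and 1730 in total. The figure is therefore a calculation for two concurrent groups. The arithmetic is not at fault.

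**Step 2. What the calculation presupposes.**

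| Reading | TAU-only | BIC | Expected suicides |
|---|---|---|---|
| 1:1 RCT | 865 | 865 | 865 × 0.03 = 25.95 against 865 × 0.01 = 8.65 |
| All receive BIC | 0 | 1730 | 1730 × 0.01 = 17.3, no comparator |

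In the single-arm reading, 17 suicides in 1730 is 0.98%, with an exact (Clopper-Pearson) 95% interval of 0.57% to 1.57%. This shows what such a study could report, namely an uncontrolled proportion. It does not measure the harm done by the contradiction. Power for the stated hypothesis is undefined when one of the two groups is absent.

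**Step 3. Power under the RCT reading.** At 865 per arm, the uncorrected normal approximation gives

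Φ[(0.02 × √865 − 0.3881) / √0.0390] = 84.5%

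Fisher's exact test gives 82.1%. The protocol's 80% is the target under the continuity-corrected formula.

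**Step 4. Illustration if some sites ran single-arm.** The protocol gives no such share, so 25% and 50% of the 1730 are assumptions. The randomised comparison would then keep 1730 × 0.75 / 2 ≈ 649 or 1730 × 0.50 / 2 ≈ 432 per arm. By the formula in Step 3, power would be about 73% or 56%.

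**The case against.** The strongest reply is that the sentence on all participants is only loose. It stands under the heading for the BIC RCT study, after a Trial design section that is explicit about two groups and about BIC going to those assigned to it. Five sections presuppose a control group. In that setting, all participants may simply mean all who are in the intervention arm. A figure belonging to the BIC Intervention section is not available here and might bear on the point.

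Much of this stands. It would be too strong to say that a site following the protocol has no control arm, because the site must follow Trial design as well. But loose wording in one section does not explain the pre-post label in the introduction, and the two agree with each other. The remark that the intervention remains unchanged could be left over from a revision towards a single-arm design, though it does not prove one.

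The same uncertainty limits the remedy. A reader might infer that the RCT is plainly intended and that the text should simply be corrected to it. The documents do not settle that: if single-arm is intended, the five RCT sections are the ones out of date. A reader might also infer that sites are already running different designs. Nothing says so. The Methodology section says only that the study is under way or being set up in four countries and invites more.

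**Conclusion.** The contradiction is real, lies in the current text, and must be resolved before the primary hypothesis can be relied on. Under the RCT reading the plan is coherent: 865 per arm, about 26 against 9 expected suicides, and power of about 82% (Fisher) to 84.5% (uncorrected normal) if the assumed 3% and 1% hold. Under the literal reading of the introduction and BIC Intervention, there is no comparator, and neither the hypothesis nor the two-group sample size can apply.

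This rests on two observations about the document: no passage limits the sentence on all participants to one arm, and none names the governing design. It does not rest on any claim about what sites have done, and the losses of power in Step 4 are conditional on assumed shares. Nor does it mean that before-after designs can never address suicide death. The limit here is that the outcome has no within-person baseline and the protocol provides no comparison cohort.

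**What to change.** State which design governs and bring all seven places into line: the introduction, Trial design, BIC Intervention, Treatment as Usual, Primary Outcome, Evaluation Procedures and Sample size.

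- **If it is the RCT**, on which the stated hypothesis, follow-up scheme and sample size already depend: relabel the study in the introduction as a multicentre 1:1 randomised controlled trial, and limit the sentence in BIC Intervention to participants randomised to the intervention arm.
- **If it is single-arm**: rewrite the hypothesis, the primary outcome and the sample size, remove the control-group text, and drop the claim against TAU on suicide death.

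In either case, report data from any site that gave BIC to everyone separately from the randomised comparison.

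The cost is an amendment and a notice to sites. Under the RCT it is two sentences if every site is already randomising. If some sites have already run single-arm, the randomised sample is smaller than 1730. Power must then be restated for the number actually randomised, or the shortfall recruited elsewhere. The single-arm route costs more, because the primary objective itself changes.

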## Treatment as Usual

Treatment as usual will be administered to all suicide attempters who are admitted to the emergency department. Suicide attempters will receive TAU per the standard guidelines at the respective emergency departments (eg: routine or systematic psychiatric and/or psychological assessment). However, TAU should be described by each site before the start of the study. The description should not be very extensive but should be precise and concise enough to analyze which treatment was given. The following information will be filled by the centers for TAU:

- a) What type of treatment they received (psychopharmacology, psychotherapy or combination)?
- b) Names and dosage for drugs prescribed or type of psychotherapy, name of therapy and number of sessions
- c) Number of suicide attempters who complied with treatment.

At 18 months after discharge, TAU's study participants will be followed up using the follow-up template in the intervention group (Annex 3).

## Assessment and Evaluation

A comprehensive assessment will be conducted before the intervention to establish a baseline for each participant. Follow-up assessments will be conducted following follow-up time.

### Primary Outcome

Hypothesis: The BIC will significantly lead to a reduced death by suicide at 18-months follow-up than treatment as usual.

Outcome measure: death from suicide at 18-month follow-up

## Secondary Outcomes

Secondary outcomes will include:

- a. Death due to other causes than suicide at 18-month follow-up.
- b. General well-being at 18-months
- c. Depressive symptoms at 18-months
- d. Sleep quality and anxiety symptoms at 18-months
- e. Social connectedness at 18 months

## Evaluation Procedures

### Evaluation procedures

Data will be collected at baseline and at 18 months follow-up for all participants. The details of the suicide attempt according to the ICD-10 codes and Medical Damage Scale (MDS) will also be evaluated at baseline along with a series of mental and physical health status.

The following scales are mandatory and will be administered at each site:

- *COVID-BIC Questionnaire (questions about Social, Economic and Health aspect)*- adopted from [https://www.iasp.info/pdf/ICSPRC\\_COVID\\_advice\\_on\\_questions.pdf](https://www.iasp.info/pdf/ICSPRC_COVID_advice_on_questions.pdf)
- *Medical Damage Rating Scale (MDRS)* which assesses the degree of medical lethality of a suicide attempt (5)
- *The Patient Health Questionnaire (PHQ-9)* which measures depressive symptoms (7)
- *Athens Insomnia Scale (AIS)* which assesses any sleep difficulty (8)
- *Generalized Anxiety Disorder (GAD-7) Scale* which measures worry and anxiety symptoms (9)
- *Multidimensional Scale of Perceived Social Support (MSPSS)* which measures perceived social support from friends, family and significant other (10)
- *Interpersonal Needs Questionnaire-15 (INQ-15)* which measures thwarted belongingness (TB) and perceived burdensomeness (PB) (11)
- *Paykel Suicide Scale (PSS)* which measures suicidal ideation and attempts (12)
- *Suicide Related Coping Scale (SRCS)* which measures measure knowledge and confidence in using internal coping strategies and external resources to manage suicidal thoughts and urges (13)
- *WHO Well-Being Scale (WHO-5)* which evaluates mood, vitality, and general interests (14)

Additional questionnaires can be added if there are additional data that a site would like to collect. However, these additional questionnaires similar to the above scales should be translated into the local language of each site, adapted to consider the cultural specificities and pilot-tested to assess the validity (if it has not been used in similar settings before).

The following socio-demographic data will be collected at baseline: age, sex, country of birth, marital status, living arrangement, residence area, employment status, education level, income level, religion affiliation and sexual orientation.

There will be follow-up contacts at nine timepoints for those in the intervention group and one follow-up at 18-month for those in the control group. These follow-ups will be conducted using a questionnaire template (Annex 3) and will follow-up if the participant is still live, any consequent suicide attempt, and the well-being of the participant.

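### Suicide deaths are found through nine contacts and a named informant in the BIC arm but one 18-month follow-up in the TAU arm, with no tracing or cause-of-death source common to both

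*Protocol*

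**What the plan says.** Primary Outcome defines the endpoint as "death from suicide at 18-month follow-up". Secondary Outcomes lists death from other causes separately, so cause of death has to be settled for each death.

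Evaluation procedures sets out "follow-up contacts at nine timepoints for those in the intervention group and one follow-up at 18-month for those in the control group". It says these contacts "will follow-up if the participant is still live, any consequent suicide attempt, and the well-being of the participant". Cause of death is not among the items named.

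BIC Intervention adds an alternative contact person, such as a friend or spouse, who "will be recorded in case volunteers are unable to reach the patient". The volunteers meant are those who make the BIC contacts.

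For the control arm, Treatment as Usual says only that at 18 months "study participants will be followed up using the follow-up template in the intervention group". It mentions no alternative contact. Evaluation procedures also states "Data will be collected at baseline and at 18 months follow-up for all participants".

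The protocol text names no death register, death certificate, hospital record search, tracing sequence or cause-of-death review for either arm. Sample size states no allowance for loss to follow-up. The annexes, including the follow-up template, are not shown.

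**The concern.** Death itself prevents the participant from responding. If the contacts are the only source, a suicide is found only when someone else can be reached. In the BIC arm, on the text as written, there is such a person, and contact during the 18 months keeps details current. In the TAU arm neither is provided for. A TAU suicide can therefore look the same as a participant who has moved or changed number.

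The endpoint is rare, so a handful of deaths missed in one arm changes the conclusion. An analysis plan can choose how to treat participants of unknown status, but it cannot supply deaths that were never ascertained. An alternative contact also cannot be obtained from a participant who has already died, so this has to be settled at enrolment.

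**Working it through.** **Inputs from the protocol.** 865 per arm; 3% suicides in TAU and 1% in BIC at 18 months; two-sided 5% level; 80% power (Sample size). 1:1 allocation (Trial design). The share of suicides missed is not given; 10%, 20% and 30% below are assumptions. The sections used do not name the primary test, so Fisher's exact test and the pooled z test are both shown.

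**1. The plan's own figure.** With a mean proportion of 0.02:

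n = [1.96·√(2·0.02·0.98) + 0.842·√(0.03·0.97 + 0.01·0.99)]² / 0.02² = 768.0.

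With the continuity correction:

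n = (768.0/4)·[1 + √(1 + 4/(768.0·0.02))]² = 865.1.

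The stated 865 is reproduced.

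**2. Expected deaths.** TAU 865 × 0.03 = 25.95, about 26. BIC 865 × 0.01 = 8.65, about 9. The whole comparison rests on about 35 deaths.

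**3. How many missed deaths matter.** Missed deaths stay in the denominator as non-events.

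| TAU vs BIC deaths found | TAU suicides missed | Fisher p | Pooled z p |
|---|---|---|---|
| 26 vs 9 | 0 | 0.0055 | 0.0037 |
| 21 vs 9 | 5 | 0.041 | 0.027 |
| 20 vs 9 | 6 | 0.059 | 0.039 |
| 19 vs 9 | 7 | 0.085 | 0.057 |

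Six missed TAU suicides remove significance by Fisher's test, and seven by the pooled z test.

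**4. Power when a share m of TAU suicides is missed.** The observed TAU rate is 0.03·(1 − m) and the BIC rate stays at 0.01 (all BIC suicides found). Power is by exact binomial enumeration at 865 per arm.

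| m | Observed TAU rate | Apparent risk ratio | Fisher power | Pooled z power |
|---|---|---|---|---|
| 0 | 3.0% | 0.33 | 82% | 87% |
| 10% | 2.7% | 0.37 | 70% | 77% |
| 20% | 2.4% | 0.42 | 55% | 63% |
| 30% | 2.1% | 0.48 | 38% | 47% |

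**5. Loss unrelated to outcome.** Suppose 20% of TAU and 5% of BIC participants are lost at random and only completers are analysed. This leaves 692 and 822 participants with expected rates still 3% and 1%. There is no bias, and pooled z power is 81.5%. Unequal loss alone is not the problem; its link to death is.

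**6. What a false benefit would require.** Take 3% in both arms, every suicide found, and a completer analysis in which 20% of TAU survivors and 5% of BIC survivors are lost. The observed rates are 0.03/(0.03 + 0.97·0.80) = 3.7% and 0.03/(0.03 + 0.97·0.95) = 3.2%. The chance of wrongly declaring a BIC benefit is 9.0% by pooled z, against a nominal 2.5%. Alternatively, with all TAU suicides found and 20% of BIC suicides missed, it is 11.8%.

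**The case against.** The strongest reply is that the arms are already aligned where it counts. Both have an 18-month assessment, TAU uses the same template, and the extra BIC contacts are the treatment under test. That is right about the contacts, which should stay. But a shared template equalises the questions asked, not the ability to find out about someone who has died.

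A second reply is that the alternative contact may be meant for both arms, and that the unseen annexes may record cause of death. This stands as a limit: that the informant is BIC-only is inferred from where it appears and from the silence of Treatment as Usual. If both arms were intended, a sentence settles it.

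Third, every miss rate above is an assumption, and the calculation gives the BIC arm perfect ascertainment. This also stands. The tables show sensitivity, not a forecast. Later linkage to death records could recover some deaths where a site has access, but the protocol does not provide for it.

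A reader might infer more than the text supports:
- **That the asymmetry readily creates a false BIC benefit.** The direct mechanism loses TAU suicides and works against BIC. The opposite needs selective loss of TAU survivors or missed BIC suicides, and nothing in the protocol points to either.
- **That TAU participants get a single call attempt.** The protocol gives one follow-up; it states no number of attempts for either arm.
- **That the same volunteer stays with a BIC participant to 18 months, or that contact mode differs by arm.** The first is not stated, and mode is described as depending on the site.

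**Conclusion.** The concern holds in this form: the protocol states no ascertainment procedure for the primary outcome that is the same in both arms, and the one it describes is weaker for TAU. The likely consequence is a diluted effect and lost power. Missing about a fifth of TAU suicides takes Fisher power from 82% to 55% (pooled z 87% to 63%) and moves the apparent risk ratio from 0.33 to 0.42.

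Confidence is high in the asymmetry of the text. The size depends on the assumed miss rates, and the direction on TAU suicides being missed more often than BIC suicides. A larger sample would not remove the bias.

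The point presupposes the two-arm randomised design in Trial design, Treatment as Usual and Sample size. The opening description of a pre-post study, and the statement under BIC Intervention that all participants receive BIC, conflict with that design and are a separate matter.

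**What to change.** In BIC Intervention, Treatment as Usual and Evaluation procedures, state that:

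1. The alternative contact person is recorded for every participant in both arms, before randomisation.
2. At 18 months the same tracing sequence is followed in both arms: the participant, then the alternative contact, then hospital or death records where the site already has access.
3. Cause of death is classified from that information, without knowledge of arm where feasible.

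The nine BIC contacts stay as they are. A different volunteer for the 18-month contact is not needed, and sensitivity outcomes can be left to the analysis plan.

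The cost is one extra field on the TAU enrolment form, effort to trace unreached participants and classify deaths, and possibly approvals for record access at some sites. No further participants or visits are needed. This is a cheap improvement, but it must be in place at enrolment to work.
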